**Visit #3 (end of Week 4) (anticipated 30 minutes in length):**

1. Investigator will measure subject's maximum/peak tongue pressure using IOPI device. 
 
o Six measurements will be taken, with 30-40 seconds between each.
 
o Mean value will be used as the subject's maximum tongue strength
 
			
2. Investigator will measure subject's regular swallowing pressures using the IOPI device. Swallows will be completed using the participant's saliva (no water or other liquid given during measurement). 
 
o Six measurements will be taken, with 30-40 seconds between each.
 
o Participants will be given 20-30 mL of water to swallow between each rep to help moisten the mouth.
 
o Mean value will be used as the subject's normal swallowing pressure
 
			
(1) No exercise	(2) Active tongue exercise	(3) Active tongue exercise + Mental practice exercise	(4) Mental practice exercise
3. Investigator instructs subject to complete 1 set (10 repetitions in each direction – open/close/lateralization/protrusion) of placebo exercise, 3x day, 3 days/week for two weeks.	3. Investigator instructs subject to complete 1 set (10 repetitions) in each direction (protrusion, elevation, left, right), 3x day, 3 days/week for two weeks. 
 
o Additional tongue depressors
 
	3. Investigator instructs subject to complete 1 set of active tongue exercise (10 repetitions) in each direction (protrusion, elevation, left, right), 3x day, 3 days/week for two weeks. 
 
o Additional tongue depressors will be
 
	3. Investigator instructs subject to complete 1 set of mental practice exercise (10 repetitions) in each direction (protrusion, elevation, left, right), 3x day, 3 days/week for two weeks.

	will be provided to subject as needed.	provided to subject as needed.  AND  Following completion of all reps of the active exercises in a given set (10 reps per direction for 40 reps total), subject will find quiet spot (without distraction) to complete mental practice exercises, including 10 repetitions per direction (40 reps) of mental practice tongue exercises. This will be repeated 3x/day, 3 days a week for 2 weeks.	
4. Investigator reminds subject to continue to complete the record form each week and to bring completed record form to next, final visit (#4).			
5. An appointment will be scheduled for Visit #4 around two weeks following Visit #3. Attempt to schedule subsequent visits at a consistent time of day, so that max measurements are taken around the same time of day each visit, preferably at the time of day the subject feels strongest.			
6. Investigator will process subject's second \$20 participation incentive.			

**Visit #4 (end of Week 6/Final session)** (anticipated 30-45 minutes in length):

1. Investigator will measure subject's maximum/peak tongue pressure using IOPI device. 
 
○ Six measurements will be taken, with 30-40 seconds between each.
 
○ Mean value will be used as the subject's maximum tongue strength
 

2. Investigator will measure subject's regular swallowing pressures using the IOPI device. Swallows will be completed using the participant's saliva (no water or other liquid given during measurement). 
 
○ Six measurements will be taken, with 30-40 seconds between each.
 
○ Participants will be given 20-30 mL of water to swallow between each rep to help moisten the mouth.
 
○ Mean value will be used as the subject's normal swallowing pressure
 

3. Investigator will collect subject's completed record form for review and storage.
4. Investigator will process subject's third (final) \$20 participation incentive.

4. Thank you letter/email will be sent to subject.

### **Statistical Analysis**

Tongue strength means (max and during swallowing) will be analyzed using SPSS in a three way mixed ANOVA.

### **5. Sample size**

It is anticipated that around 20-30 subjects will be recruited to participate in this study at USFSM.

### **6. Study Population or inclusion and exclusion criteria**

Participants will be healthy older adults without a history of swallowing problems or neurological disorders. Inclusion/exclusion criteria are stated below.

Inclusion criteria include:

- Adults aged 60-89
- < 3 on EAT-10 (part of health questionnaire)
- Mean of  $\geq 2.5$  on the KVIQ-10 questions (Kinesthetic and Visual Imagery Questionnaire, short version), a screening questionnaire that assesses a person's motor imagery abilities
- $\geq 24$  on MMSE (Mini Mental State Examination), a screening questionnaire that assesses cognitive abilities.
- Availability to complete a consecutive 6-week exercise regimen
- There are certain conditions that are common to the aging study population we are recruiting which will be acceptable: controlled hypertension and controlled diabetes mellitus

Exclusion criteria include:

- History of diagnosed dysphagia (swallowing disorder)
- History of a seizure(s)
- Current or past problem with pain disorders involving the jaw muscles or joint of the mandible (e.g., TMJ disorder or myofascial pain disorder) – these are contraindicated for tongue strengthening exercises
- Presence of oral piercings/oral apparatus that may interfere with tongue exercises
- Medical conditions that would affect oral motor performance (e.g., history of acute or degenerative neurological condition, head/neck cancer), as determined by investigator
- History of a diagnosed dementia or other cognitive impairment
- Uncontrolled high blood pressure
- Visual impairment that would prevent the subject from independently viewing written mental exercise instructions and visual images, corrected contacts or lenses are acceptable

- Hearing impairment that would prevent the subject from receiving verbal instruction from investigators
- Motor impairment or injury that would interfere with subject's ability to independently manipulate a lightweight, portable counter clicker tool or perform jaw exercises.
- English is not the person's primary language

No potential subject will be disqualified based on information regarding ethnicity, race, gender, sex, or socioeconomic status information.

## **7. The expected results of the research, such as reports, papers, and contributions to theory**

It is anticipated that the results of the proposed research study will significantly contribute to the field of speech-language pathology, both in its pioneered innovation as an approach not yet explored for muscles important to swallowing and as a potential therapeutic intervention technique that may advance patient care. Further, the results of the study may also inform preventative wellness and care in speech-language pathology, as the normal aging process can include lingual weakening and dysphagia in the typical aging population, in those without a contributing disease process. Data may be presented at national/international conferences. Data may be published in peer-reviewed journals. Data may be used as pilot data for grant applications. The audience interested in our reported work will include speech-language pathologists, rehabilitation specialists, neuropsychologists, and neurologists.

## **9. Any potential risks to the subjects**

There is no known risk for motor imagery exercises. There are no known risks for oral motor exercises (tongue strengthening exercises).

## **10. Any experimental procedures or interventions that will be implemented**

Study groups will include: 1) placebo (jaw exercises with relaxation exercises), 2) active tongue exercises only, 3) active tongue exercise + motor imagery of tongue exercises, and 4) motor imagery of tongue exercises only. Experimental interventions include groups 3 and 4.

## **11. Any potential benefits to subjects**

Depending on group assignment, participants will be participating in a tongue strengthening protocol, which may have specific swallowing related benefits; however, this will not be directly measured and there is no guarantee of any swallow related benefit.

## **12. Human subjects considerations including · description of the informed consent process; · discussion of how the privacy and confidentiality of the subjects will be maintained.**

Participation will be entirely voluntary and an extensive inclusion/eligibility screening process will be completed prior to the informed consent process. Consent will be obtained prior to the screening process (both over the phone and/or via email/mail prior to obtaining the Screening Inclusion-Eligibility and EAT-10 screening forms completion and prior to beginning the in-person screening session). Should a participant qualify for the study, the informed consent form will be reviewed with the subject, providing ample time as needed to answer subject questions prior to voluntary signature. The privacy and confidentiality of the participants will be maintained. Telephone screenings and in-person visits will be completed in private and confidential locations. All data will be stored on [name] password-protected USFSM laptop. Study files on this laptop will also be password-protected. The data on the laptop will be encrypted for protection, in case the laptop is lost or stolen. Each subject's identity will be disassociated from the subject's personal data - a subject number will be assigned to each subject upon signing of the informed consent. Physical data (e.g., subject record forms) will be identified according to subject number as much as possible. All physical data will be stored in a locked desk cabinet in the secure and locked office of the investigator. Only [name] will have access to the desk cabinet key.

Tongue strength measures from each of the four sessions will be recorded on paper forms for convenience and transferred to a digital spreadsheet after each session. Participant record forms for weeks of practice will be in paper format. All paper forms will be identified only by participant ID. Tongue strength measures (kPa) will be transferred to a digital spreadsheet (de-identified). Participant record forms (de-identified) will be scanned into digital format. De-identified paper forms will be stored in a locked file cabinet in [name] office, which requires lock/key access. Spreadsheets of tongue strength measures will be stored on [name] USFSM laptop, which is password protected and requires permission by [name] to access. Non-USFSM researchers at JMU and LLU will have access to de-identified digital data in spreadsheet format. De-identified data will be shared between universities using a password protected Dropbox account. The only identifiable information that will be shared between study sites will include participants' first/last names and email addresses so that the USFSM study site can process participant incentives in the form of Amazon gift cards. The JMU, LLU, and TCU study site principal investigators will send [name] individual participant names and emails included in an encrypted Word document, which will be used to generate an Amazon gift card as payment for the completed session, according to the compensation schedule above. As participants get paid in three installments, this will be done three times for each participant. [name] will delete the encrypted file as soon as the gift card is sent by email. All other study data will remain shared in de-identifiable form only.

Only de-identified data will be kept after the project ends. Consent forms will be destroyed five years after publication.

**13. If the study is greater than minimal risk, describe the data and safety monitoring plan, whether or not there is a data and safety monitoring board, how often data will be reviewed for safety, early stopping criteria, etc.**

We do not anticipate the study involving greater than minimal risk. Participation will be entirely voluntary and subjects will be allowed to opt-out of the study at any time.

- 3. Does a 6 week treatment of motor imagery tongue exercises with or without active tongue exercise alter cortical hemodynamic response patterns in healthy older adults compared to a 6 week treatment of placebo exercises and 6 week treatment of active tongue strengthening exercises? (JMU participants only) (secondary outcome)

2. Description of Participants

Participants will be healthy older adults without a history of swallowing problems or neurological disorders. Inclusion/exclusion criteria are stated below.

Inclusion criteria include:

- Adults aged 60-89
- < 3 on EAT-10 (part of health questionnaire)

- Mean of ≥2.5 on the KVIQ-10 questions (Kinesthetic and Visual Imagery Questionnaire, short version), a screening questionnaire that assesses a person's motor imagery abilities
- \geq 24 on MMSE (Mini Mental State Examination), a screening questionnaire that assesses cognitive abilities.
- Availability to complete a consecutive 6-week exercise regimen
- There are certain conditions that are common to the aging study population we are recruiting which will be acceptable: controlled hypertension and controlled diabetes mellitus

Exclusion criteria include:

- History of diagnosed dysphagia (swallowing disorder)
- History of a seizure(s)
- Current or past problem with pain disorders involving the jaw muscles or joint of the mandible (e.g., TMJ disorder or myofacial pain disorder) these are contraindicated for tongue strengthening exercises
- Presence of oral piercings/oral apparatus that may interfere with tongue exercises
- Medical conditions that would affect oral motor performance (e.g., history of acute or degenerative neurological condition, head/neck cancer), as determined by investigator
- History of a diagnosed dementia or other cognitive impairment
- Uncontrolled high blood pressure
- Visual impairment that would prevent the subject from independently viewing written mental exercise instructions and visual images, corrected contacts or lenses are acceptable
- Hearing impairment that would prevent the subject from receiving verbal instruction from investigators
- Motor impairment or injury that would interfere with subject's ability to independently manipulate a lightweight, portable counter clicker tool or perform jaw exercises.
- English is not the person's primary language

No potential subject will be disqualified based on information regarding ethnicity, race, gender, sex, or socioeconomic status information.

3. Sample size

It is anticipated that around 40 participants will be recruited to participate in this study across all study sites (around 10 per study group total). As this is a novel pilot study, a power analysis will be conducted using data collected from this investigation when 10 participants have completed the study.

4. Primary Analysis/Results

The investigators hypothesize, based on previous research in the area of motor imagery, that the group receiving both active and MI treatment will make the most gains in all three measures, followed by the active only group, then the MI only group, then the placebo group (control).

Tongue strength means (max and during swallowing) will be analyzed using SPSS in a three way mixed ANOVA. The significance level will be set at $\alpha = .05$.

5. Other Pre-specified Analysis/Results

The investigators will also be looking at cortical hemodynamic response patterns to motor imagery and physical execution of active tongue strengthening exercise between groups with JMU participants only. As this is exploratory in nature, the current investigators are not including a specific hypothesis. Rather, observational/descriptive/proof of concept factors will be explored. If sufficient data is available, a three-way mixed ANOVA will be used to understand effects on percent change in oxygenation during hemodynamic response.

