Our hypothesis, based on previous research, is that the group receiving both active and MI treatment will make the most gains in all three measures, followed by the active only group, then the MI only group, then the placebo group (control).

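### The plan predicts a full ranking of the four arms, but its only stated test ignores order, so a significant result would neither support the ranking nor identify an imagery effect.

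*SAP*

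**What the plan says.** SAP section 4 (Primary Analysis/Results) states the hypothesis "that the group receiving both active and MI treatment will make the most gains in all three measures, followed by the active only group", then imagery only, then placebo. Protocol section 3 gives the same complete order: the combined group "will make the most gains in all three measures, followed by the active only group, then the MI only group, then the placebo group (control").

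The test follows in one SAP sentence: "Tongue strength means (max and during swallowing) will be analyzed using SPSS in a three way mixed ANOVA". The next sentence fixes the threshold: "The significance level will be set at" .05. The Statistical Analysis paragraph of the protocol has the same ANOVA sentence and nothing more. The three factors are not named. Neither document gives a planned contrast, a trend test, a pairwise or post hoc comparison, or a rule for deciding that the ranking is supported.

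SAP section 3 plans around 40 participants, "around 10 per study group total", and gives no effect size, SD or power. SAP section 1 labels both pressure outcomes primary. Its research questions ask how imagery, with or without active exercise, compares with placebo and with active exercise.

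**The concern.** The hypothesis is directional and ordered; the test is neither. An omnibus F statistic is unchanged when the arms are relabelled, so it comes out the same for the predicted ranking, its exact reverse or any shuffle. A significant F could arise because tongue exercise works and imagery does nothing.

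The plan then leaves only two routes to a statement about the ranking: reading the order of the observed means, or choosing comparisons once the data are known. The first is unreliable at 10 per arm. The second is what a pre-specified plan should prevent. An unordered test also spreads its sensitivity over patterns that the investigators do not expect, which costs power if their prediction is right.

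**Working it through.** **Inputs.** From the SAP: four arms, about 10 per arm, alpha .05. The arithmetic agrees: 4 × 10 = 40. N = 40 cannot be derived from a power formula, because no effect size, SD or power is stated. Assumed here: SD 1 for the analysed pressure, no dropout, two-sided tests, and the mean patterns below. Arms are listed as placebo / imagery only / active only / combined.

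**Formulas.** For the group F test (3 and 36 df), the noncentrality is λ = n Σ(μᵢ − μ̄)² / σ². For the ordered contrast with weights −3, −1, +1, +3 (36 df), it is δ = Σcᵢμᵢ / (σ√(Σcᵢ²/n)), with Σcᵢ² = 20, so the denominator is √2 = 1.414.

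**The F test is blind to order.** Means 0, 1/3, 2/3, 1 give λ = 10 × 0.5556 = 5.56 and 44% power. Reversing or shuffling them leaves λ and the power unchanged.

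**Equal steps in the predicted order.**

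| Placebo-to-combined spread | λ | F test | δ | Ordered contrast |
|---|---|---|---|---|
| 0.8 SD | 3.56 | 29% | 1.89 | 45% |
| 1.0 SD | 5.56 | 44% | 2.36 | 63% |
| 1.2 SD | 8.00 | 60% | 2.83 | 79% |

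**Other patterns, largest difference 1.0 SD.**

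| Pattern | Means | F test | Ordered contrast |
|---|---|---|---|
| Only active exercise works | 0/0/1/1 | 71% | 79% |
| Only the combination works | 0/0/0/1 | 57% | 54% |
| Combined worse than active alone | 0/0/1/0.5 | 53% | 41% |
| Imagery works, active exercise adds nothing | 0/1/0/1 | 71% | 28% |
| Only imagery alone works | 0/1/0/0 | 57% | 11% |

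**If the target is a group-by-visit interaction.** With four arms and four visits it has 3 × 3 = 9 df. In simulation (equal steps, linear gains, correlation 0.5 between visits, 6,000 runs) its power is 21% at 0.8 SD and 34% at 1.0 SD. An ordered contrast on final minus baseline has 46% and 64%.

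**Reading the order of the means.** If each true gap is 0.3 SD, the four observed means fall in the predicted order about 35% of the time. With no effect at all they do so about 4% of the time (1 in 24).

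**Single steps.** Before baseline adjustment, the 95% interval for an adjacent difference has half-width 2.028 × √(2/10) = 0.91 SD. A true step of 1/3 SD would be detected about 11% of the time.

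**Baseline adjustment.** Adjusting for baseline multiplies the SD by √(1 − ρ²). At a 1.0 SD spread with equal steps and 35 df, δ becomes 2.357/0.866 = 2.72 (75% power) for an assumed ρ of 0.5, and 2.357/0.714 = 3.30 (89%) for ρ of 0.7. The unadjusted Week 6 figure is 63%.

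**The case against.** This is a pilot meant to guide later work. An omnibus ANOVA followed by a description of the means is conventional, and a linear trend is one option among several. The research questions ask for particular arm comparisons, which a trend does not answer. The ANOVA's factors are unnamed, so a three-degree-of-freedom Week 6 test is a stand-in for the planned analysis. Much of this stands. The power figures illustrate the loss and do not measure it for the actual test. The pilot label lowers the stakes, although the SAP still names primary outcomes, a directional hypothesis and an alpha level.

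A reader might infer that the ordered contrast should replace the ANOVA at almost no cost, because the loss is only about 3 points if the combination alone works (54% against 57%). That is one favourable pattern. If imagery works and active exercise adds nothing, the loss is 43 points (71% to 28%), and the documents contain nothing that rules this pattern out.

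A reader might also infer that a significant contrast would confirm the ranking. It would not: the contrast reaches 79% power when only active exercise works, a pattern in which two of the three predicted steps are absent and imagery has no effect.

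Finally, a contrast on raw Week 6 pressure would itself fit the hypothesis poorly. The prediction concerns gains, and baseline pressure is measured at Visit 1.

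**Conclusion.** The mismatch is real and does not depend on which three factors are meant: every group or group-by-visit F test ignores order, and neither document adds anything that looks at order or at particular arms. Followed exactly, the plan cannot support its own hypothesis.

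The size is conditional. With 10 per arm, SD 1, equal steps and a spread of 0.8 to 1.2 SD, the ordered contrast gains about 16 to 19 points. The gain shrinks or vanishes when three arms nearly tie, and it reverses when the true order departs from the prediction.

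The documents do not support the stronger claims that the ANOVA is invalid, that a definite amount of power is lost, or that one trend test would settle the ranking. The contrast is a worthwhile addition as a test of trend. What imagery contributes has to be read from imagery against placebo and combined against active alone, both of which the research questions call for. The change should be made: it is cheap and closes a clear gap.

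**What to change.** Keep the ANOVA and add to SAP section 4:

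> For each pressure outcome, one pre-specified ordered contrast (placebo −3, MI only −1, active only +1, active + MI +3), two-sided, is applied to Week 6 pressure adjusted for baseline, as a test of trend in the predicted direction. The adjacent-arm differences (MI only v placebo, active only v MI only, active + MI v active only) are reported with 95% confidence intervals. The trend is not read as proof of the full ranking or of an imagery effect; an imagery effect is judged from the MI only v placebo and active + MI v active only differences.

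This takes a paragraph of SAP text and a contrast line in SPSS; no new data are needed. It has three costs. There is one extra test per outcome. Intervals for single steps will be wide, with a half-width of about 0.9 SD before baseline adjustment. The contrast also has low power if the true pattern departs from the predicted order, which is why it is added to the ANOVA and does not replace it.
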